## Protocol amendment /Revision History

Protocol Version and Date	New text
0.4	Version for submission to IRAS
0.5	REC recommendations included
0.6	REC recommendations included

**SPONSOR:** Congenica Ltd

## 1 List of abbreviations

CI Chief Investigator
CRF Case Report Form
GCP Good Clinical Practice
ICF Informed Consent Form
ISF Investigator Site File

NHS R&D National Health Service Research & Development

PI Principal Investigator

PIS Participant Information Sheet **RCT** Randomised Controlled Trial **REC** Research Ethics Committee SDV Source Document Verification Standard Operating Procedure SOP SSA Site Specific Assessment **TMG Trial Management Group Trial Steering Committee TSC** 

PGx Pharmacogenomics

REC ID: 21/PR/0673

ISRCTN: temp ID 39821

# 3 Study synopsis

Brief title:	HAPPY
Official title:	Health Aging Pharmacogenetics and PolypharmacY
Sponsor reference number:	100258
Public database identifier	**tbc
Study design	Case series/case note review; Feasibility/pilot study; Questionnaire, interview or observation study
Study Population/disease condition	Over 50 years old on multiple medications for cardiovascular disease, pain control, mental health and gastro protection.
Eligibility criteria:	
 
Inclusion criteria:
 
Over 50 years of age.
 
Taking 3 or more medicines.
 
The clinical areas we will focus on will include cardiovascular health, pain (musculoskeletal) gastro protection and mental health
 
Who agree to follow up after pharmacogenetics analysis.
 
Exclusion criteria:
 
Who do not have the capacity to consent to take part in the project and
 
Who are suffering from terminal cancer or terminal disease
 
Pregnant
 
Suffering from severe mental illness
 
Under the age of 50 years
 
Are not able to understand English or translated material
 
Who do not agree to follow up after pharmacogenetics analysis and in particular those patients who have actionable pharmacogenetics.
 

Target number of participants	500 over 20 months

# Criteria for evaluation

## Primary outcome measure(s)

Number of currently actionable DNA variants per patient.

- The number of patients with currently actionable variants identified.
- Rate of recommendations for prescription changes
- The prescribing decisions made on receipt of the PGx data.
- Factors contributing to whether recommendations are or are not converted to medication change within the medication review

REC ID: 21/PR/0673

ISRCTN: temp ID 39821

	Secondary outcome measure(s)
	# and type of adverse effects reported by patients pre and post receipt of
	# Actionable PGx variants which do not impact on current medication Anxiety measures at baseline, 1 mth, 3 mths, 6 mths and 1 year after consent Patient acceptance of the use of PGx The time taken to process and receive DNA/PGx results from the time of consent to the project. Fraility index measures at baseline, 1 mth, 3 mths, 6 mths and 1 year after consent Service use review (eg. #hospital admissions, GP appointments and recorded adverse effects at baseline and 1 year)
Sources of funding	The trial is funded by Congenica Ltd and Innovate UK.
Anticipated start date:	September 2021
Anticipated primary completion date:	April 2023
Sponsor	Congenica
Key Contact names	Chief Investigator: [name] Email: [contact] [contact] Fax: n/a  Sponsor representative: [contact]

HAPPY\_Protocol\_v0.6 IRAS project ID: 295387

## 4 Background

Polypharmacy, the use of multiple medications (3 or more) at the same time is common amongst older individuals and/or in people with multiple co-morbidities. In these populations, medicines are frequently associated with adverse drug reactions (ADRs), falls risk and may have a negative impact on both cognition and quality of life. There are an estimated 237M medication errors per year in the NHS (England), with 66M of these potentially clinically significant.

"Definitely avoidable" adverse drug reactions collectively cost ~£100M annually, contribute to ~1700 deaths/year and are directly responsible for an additional ~700 deaths/year. Evidence demonstrates that over 40% of ADR-related hospital admissions may be preventable.

Pharmacogenomics (PGx), the study of how genes affect an individual's response to drugs, aims to provide information to improve safety and effectiveness of drug treatment. Pharmacogenomic information can be considered actionable if it leads to a change in prescribing decisions, such as alternative medications or dosing. PGx has been shown to be effective for preventing potential side effects of polypharmacy. As a strategy for optimizing medication usage, PGx is becoming an important element of precision medicine with significant potential impact in older people with polypharmacy.

This research study aims to investigate the use of a PGx-led approach to the management of polypharmacy. The aim is to assess outcomes e.g., actionable PGx DNA sequence variants, deprescribing, reduced ADRs and effect on number and length of hospital admissions and General Practice (GP) visits.

## 5 Study objectives

#### 5.1 Primary objective

The use of innovative technology, scientific and clinical expertise available through this programme of work will enable us to study and understand how we can use genetic data in day-to-day clinical General Practice. This particularly applies to those patients with complicated medical problems and includes patients on multiple drug treatment treating long term medical conditions such as diabetes and cardiovascular disease. PGx is the study of how genes affect an individual's response to drugs and aims to provide information to improve safety and effectiveness of drug treatment. If we can identify those patients who are at risk of adverse drug effects by virtue of their genetic make up then we may be able to pre-emptively prescribe at doses that take into account genetic information with clinical prescribing protocols and thus reduce side effects.

There is a paucity of studies that have assessed implementation of pharmacogenomics in primary care and its implementation in association with polypharmacy. The principle of using information on gene variants that lead to new actionable clinical management is important clinically and may provide information that leads to patient safety through reduction of adverse drug effects. However the implementation and use of pharmacogenomic information in clinical General Practice in the NHS requires integration with current workflows including the recording of pharmacogenomic data on clinical decision support systems, be readily available and require relationship based, shared decision making care.

This innovative study brings together the scientific analysis of genetics relating to commonly

prescribed drugs used in the clinical areas of cardiovascular disease, pain control, mental health and gastro protection.

### 5.2 Secondary objectives

If the first research question is how do we generate pharmacogenomic data and integrate it with current workflows and data recording in clinical general practice then the next question is how we measure the effect of using pharmacogenomic data. There is a need to use established techniques including patient questionnaire .

Participants can optionally consent for use of data in future health research projects, and for validation and improvement of diagnostic testing methods.

## 6 Trial design

Case series/case note review; Feasibility/pilot study; Questionnaire, interview or observation study

## 7 Participation selection criteria

There will be no exceptions (waivers) to eligibility criteria prior to participant inclusion into the study. Any questions raised about eligibility should be addressed prior to entering the participant.

The eligibility criteria have been carefully considered and are standards used to ensure the trial results can be appropriately used to make future decisions for other people with similar disease or medical condition. It is therefore vital that exceptions are not made to thefollowing detailed selection criteria.

Participants will be considered eligible for enrolment into this study if they fulfil the inclusion criteria and none of the exclusion criteria as defined below.

Eligible participants will be assigned a Trial specific Identification number in a pre-agreed format in accordance with Site Identifier and next sequential numerical value, e.g. PGx\_Ban\_001.

#### 7.1 Inclusion criteria

- Over 50 years of age.
- Taking 3 or more medications for cardiovascular health, pain (musculoskeletal) gastro protection and mental health
- Agree to follow up after pharmacogenetics analysis.

#### 7.2 Exclusion criteria

- Do not have the capacity to consent to take part in the project
- Suffering from terminal cancer or terminal disease.
- Pregnant
- Suffering from severe mental illness.
- Under the age of 50 years.
- Not able to understand English or translated material
- Do not agree to follow up after pharmacogenetics analysis and in particular those patients who have actionable pharmacogenetics.

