## 9 Study procedures

#### 9.1 Informed consent

It is essential that all trial teams undertaking the informed consent process have signed the Sponsor's Delegation of Responsibilities Log to ensure that the person has been delegated the responsibility by the study CI/PI.

Informed consent will be obtained from eligible participants by a member of the research team after confirming the eligibility, inclusion and exclusion criteria.

The Principal Investigator or designee will explain to the participant that they are under no obligation to enter the trial and can withdraw at any time during the trial, without having to give a reason. Those who agree to take part will be asked to sign a Consent Form prior to any study investigation or treatment.

A copy of the signed Informed Consent Form (ICF) along with a copy of the most recent approved Patient Information Sheet (PIS) will be given to the study participants. An original signed & dated ICF will be retained. Consent will be documented in the OpenApp study registry.

If new information results in significant changes to the risk-benefit assessment, the ICF will be reviewed and updated as necessary. All participants, including those already enrolled in the study, will be informed of the new information, given a copy of the revised ICF and askedto re-consent if they choose to continue in the study.

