#### 9.3 Discontinuation/withdrawal of participants and stopping rules

In consenting to the study, participants are consenting to a saliva sample. However, an individual may withdraw from the study for anyone of the following reasons:

Intercurrent illness that prevents further protocol treatment

Any change in participant's condition that in the investigator's opinion justifies discontinuation.

Withdrawal of consent by the participant

As participation in the study is entirely voluntary, the participants may choose to discontinue involvement at any time without penalty or loss of benefits to which they may be entitled. Although not obliged to give a reason for discontinuing their participation, a reasonable effort should be made to establish this reason, whilst remaining fully respectful of the participants' rights. Participants who discontinue study participation for any of the above reasons should remain in the study for the purpose of follow-up and data analysis.

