## 15 Statistical design

#### a. Endpoints

## 15.1.1 Primary endpoints

The number of patients with currently actionable variants identified.

- Rate of recommendations for prescription changes
- The prescribing decisions made on receipt of the Pgx data.
- Factors contributing to whether recommendations are or are not converted to medication change within the medication review.

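### The last exclusion criterion names a genotype result that cannot exist when eligibility is checked, and section 9.3 as worded keeps people who have withdrawn consent in follow-up

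*Protocol*

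**What the plan says.** The last exclusion criterion in Protocol section 7.2 reads "Do not agree to follow up after pharmacogenetics analysis and in particular those patients who have actionable pharmacogenetics". The synopsis repeats it: "Who do not agree to follow up after pharmacogenetics analysis and in particular those patients who have actionable pharmacogenetics". The matching inclusion criterion in section 7.1 has no genotype clause: "Agree to follow up after pharmacogenetics analysis". The opening of section 7 allows no waivers.

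Section 9.1 sets the order of events: "Informed consent will be obtained from eligible participants by a member of the research team after confirming the eligibility, inclusion and exclusion criteria", and then "Those who agree to take part will be asked to sign a Consent Form prior to any study investigation or treatment". Under section 10.3 the genotype comes from a saliva sample that is sent to a laboratory, processed and turned into a PGx report.

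For people already enrolled, section 9.3 lists reasons for stopping, one of which is "Withdrawal of consent by the participant". It then says: "Participants who discontinue study participation for any of the above reasons should remain in the study for the purpose of follow-up and data analysis". Section 9.1 tells participants that they may withdraw at any time without giving a reason, and section 9.3 itself says they may stop at any time.

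The first primary endpoint in section 15.1.1 is "The number of patients with currently actionable variants identified". It is a count, and the section gives no denominator.

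**The concern.** An eligibility rule should use only what is known when eligibility is decided. This one points to a result that arises after enrolment. A site that tries to obey it, with no waivers allowed, can do so only by taking out an enrolled participant once the report shows an actionable variant and that person declines follow-up. That makes membership of the analysed group depend on the quantity the study sets out to count.

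Section 9.3 gives the opposite instruction for enrolled participants, so two sites could treat the same person differently and each cite the protocol. Section 9.3 also has a fault of its own. Its retention rule covers every listed reason, and so includes people who have withdrawn consent. Continued follow-up of those people does not fit the right to withdraw that sections 9.1 and 9.3 describe.

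**Working it through.** **Order of events.** Eligibility is confirmed (9.1), then consent is signed (9.1), then the sample is taken and genotyped (10.3), then the report reaches the GP. Actionable status appears only at the last step. At the first step the genotype clause can identify nobody. Used at the last step, it removes by result.

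**Figures in the plan.** The target of 500 (synopsis, section 15b) is justified by feasibility. No expected rate, precision or dropout is given, so there is no calculation to reproduce.

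**Illustration of removal after the result.** Inputs:
- N = 500, from the protocol.
- p, the true share with an actionable result: assumed.
- d1 and d0, the shares removed for declining follow-up among carriers and non-carriers: assumed.

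Observed proportion = p(1 − d1) / [p(1 − d1) + (1 − p)(1 − d0)].

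| p | d1 | d0 | Actionable / kept | Observed | Shift (points) |
|---|---|---|---|---|---|
| 30% | 10% | 0 | 135/485 | 27.8% | −2.2 |
| 30% | 20% | 0 | 120/470 | 25.5% | −4.5 |
| 50% | 10% | 0 | 225/475 | 47.4% | −2.6 |
| 50% | 20% | 0 | 200/450 | 44.4% | −5.6 |
| 60% | 10% | 0 | 270/470 | 57.4% | −2.6 |
| 60% | 20% | 0 | 240/440 | 54.5% | −5.5 |
| 50% | 20% | 10% | 200/425 | 47.1% | −2.9 |
| 50% | 10% | 10% | 225/450 | 50.0% | 0 |

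For scale, the 95% half-width 1.96 × √(p(1 − p)/500) is 4.0 points at p = 30%, 4.4 at 50% and 4.3 at 60%. Removing 20% of carriers alone would shift the proportion by more than sampling error at that size. Removing 10% would shift it by roughly half as much. The protocol sets no precision target, so this comparison is only a yardstick.

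The count behaves differently from the proportion. At p = 50% it falls from 250 to 225 when 10% of carriers are removed, whatever happens to non-carriers.

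**Section 9.3 followed literally.** If every discontinuer stays in the analysis, d1 = d0 = 0 and the shift is zero.

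**The case against.** The criterion can be read as a clumsy prospective commitment: at entry, the person must agree to be followed up, above all if the result proves actionable. Section 9.1 applies eligibility at entry, no section describes removal after a result, and the reasons listed in 9.3 include neither genotype nor later ineligibility. On that reading nobody is lost. This stands, and it is why the bias is only conditional. But section 7.1 already asks for that agreement, so on this reading the genotype words add nothing except the risk of being applied later.

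The criterion also covers all who decline, and its last half adds emphasis without limiting the rule to carriers. Equal removal does not bias a proportion. This stands too.

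A reader might infer that 7.2 and 9.3 together bias the result. They do not: 9.3, if followed, keeps these participants in and prevents the bias. A reader might also infer that dropping those who decline follow-up raises the rate at which recommendations become medication changes. The documents do not support that. Section 15.1.1 places conversion within the medication review, the follow-up questionnaires from 1 to 12 months come after that review (10.2), and prescribing is the physician's decision (10.5). Declining questionnaires does not show refusal of a change.

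Finally, analysis sets are commonly left to a SAP, and the consent pages, which may say what happens to data after withdrawal, are not available here. Neither omission is held against the protocol. The point concerns two rules that it does state.

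**Conclusion.** Two rules are wrong as written. The exclusion criterion refers to a status that cannot exist when it is applied. The retention rule in 9.3 takes in people who have withdrawn consent, contrary to the right stated in the same section and in 9.1.

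The effect on the primary endpoint is a risk and is not established. It arises only if a site applies the clause after the report. The count of actionable patients then falls. The proportion, which is a natural summary although section 15.1.1 names only a number, is biased downward if carriers are removed more often than non-carriers. The size is about 2 to 5.6 points for p of 30–60% with 10–20% of carriers removed and no one else, and zero under equal removal. The protocol gives none of p, d1 or d0, so these figures show scale and do not estimate what will happen.

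**What to change.** 1. In section 7.2 and the synopsis, delete the words of the last exclusion criterion from 'and in particular' onward. Assess agreement to follow-up once, at consent, as section 7.1 already implies.
2. State that nobody is removed because of the genotype result or a later refusal of follow-up, so that every consented participant with a PGx result counts in the primary endpoint.
3. In section 9.3, exempt withdrawal of consent from the rule that discontinuers remain in the study. After withdrawal no new data are collected, and data gathered before it are retained as the consent form allows. Other discontinuers stay in as now.

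Changes 2 and 3 belong together. Once withdrawal of consent is exempted, the current retention sentence no longer protects the count for those people, and change 2 does so as far as the consent form permits.

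The cost is a few lines in three places, and possibly a tick-box on the withdrawal form. Sample size, visits and data collection for other participants are unaffected.

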## 8 Participant Recruitment process

Patient recruitment will commence only once there is evidence that the following approval/essential documents are in place:

- 1. REC and HRA approval
- 2. Final sponsorship and host site confirmation

All subjects who wish to enter the study will be fully screened and consented appropriate delegate of the Chief Investigator.

Potential participants will be identified by two participating General Practices based on the inclusion criteria. The practices use EMIS and SystmOne electronic health record (EHR) systems. Searches across the databases are a routine part of clinical General Practice and practice staff who provide direct care team in the practices who have expertise in data searches will identify potential participants across the 4 chosen clinical areas.

The study will be conducted by the sponsor, participating sites and all investigators in accordance with the protocol, the Declaration of Helsinki, the guidelines on Good Clinical Practice (GCP) and all legal requirements, including applicable national legislation, for the conduct of this study.

## 9 Study procedures

#### 9.1 Informed consent

It is essential that all trial teams undertaking the informed consent process have signed the Sponsor's Delegation of Responsibilities Log to ensure that the person has been delegated the responsibility by the study CI/PI.

Informed consent will be obtained from eligible participants by a member of the research team after confirming the eligibility, inclusion and exclusion criteria.

The Principal Investigator or designee will explain to the participant that they are under no obligation to enter the trial and can withdraw at any time during the trial, without having to give a reason. Those who agree to take part will be asked to sign a Consent Form prior to any study investigation or treatment.

A copy of the signed Informed Consent Form (ICF) along with a copy of the most recent approved Patient Information Sheet (PIS) will be given to the study participants. An original signed & dated ICF will be retained. Consent will be documented in the OpenApp study registry.

If new information results in significant changes to the risk-benefit assessment, the ICF will be reviewed and updated as necessary. All participants, including those already enrolled in the study, will be informed of the new information, given a copy of the revised ICF and askedto re-consent if they choose to continue in the study.

#### 9.2 Randomisation procedure

There is no need for randomisation in this study.

#### 9.3 Discontinuation/withdrawal of participants and stopping rules

In consenting to the study, participants are consenting to a saliva sample. However, an individual may withdraw from the study for anyone of the following reasons:

Intercurrent illness that prevents further protocol treatment

Any change in participant's condition that in the investigator's opinion justifies discontinuation.

Withdrawal of consent by the participant

As participation in the study is entirely voluntary, the participants may choose to discontinue involvement at any time without penalty or loss of benefits to which they may be entitled. Although not obliged to give a reason for discontinuing their participation, a reasonable effort should be made to establish this reason, whilst remaining fully respectful of the participants' rights. Participants who discontinue study participation for any of the above reasons should remain in the study for the purpose of follow-up and data analysis.

#### 9.4 Definition of the End of Trial

The study will be completed at the receipt of the sample of the last recruited patient, or at the end of 20 months. The REC and the Sponsor will be notified of the end of study within 90 days of its planned completion or within 15 days if the study is terminated early.

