#### 10.2 Questionnaire

Information on patients adverse reactions will be gathered in the form of review of patient records by their GP and questionnaires at multiple timepoints throughout the study; pre-PGx report, 1 month, 3 month, 6 month and 12 month post-medication review (see appendix 1). This will include capture of data on number of GP visits, medication use, hospital admissions, adverse drug reactions

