#### 15.1.2 Secondary endpoints

# and type of adverse effects reported by patients pre and post receipt of PGx data # Actionable PGx variants which do not impact on current medication Anxiety measures at baseline, 1 mth, 3 mths, 6 mths and 1 year after consent Patient acceptance of the use of PGx

The time taken to process and receive DNA/PGx results from the time of consent to the project. Fraility index measures at baseline, 1 mth, 3 mths, 6 mths and 1 year after consent Service use review (eg. #hospital admissions, GP appointments and recorded adverse effects at baseline and 1 year)

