#### b. Sample size calculation

We aim to recruit 500 families over the course of 15 months at two sites. This is a realistic number of eligible cases based on inclusion criteria. By the end of this time we will have enough proof-of-principle data to enable design and execution of an appropriately powered clinical study.

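### The end-of-trial rule closes the study before its own 1-year assessments can be collected for much of the sample

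*Protocol*

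**What the plan says.** Section 9.4 of the Protocol gives two triggers for completion: "The study will be completed at the receipt of the sample of the last recruited patient, or at the end of 20 months". It does not say which prevails if they differ.

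The follow-up that has to fit inside that limit is set elsewhere:

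- Section 15.1.2 lists "Anxiety measures at baseline, 1 mth, 3 mths, 6 mths and 1 year after consent", the same schedule for the frailty index, and service use including "GP appointments and recorded adverse effects at baseline and 1 year". Anxiety and frailty are timed from consent. Service use has no stated origin.
- Section 10.2 schedules questionnaires and GP record review at "pre-PGx report, 1 month, 3 month, 6 month and 12 month post-medication review". Here the clock starts at the medication review, which follows the PGx report.

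The recruitment period appears twice. Section 15b says: "We aim to recruit 500 families over the course of 15 months at two sites". The synopsis, in its row for the target number of participants, says "500 over 20 months". The synopsis also gives September 2021 as the anticipated start and April 2023 as the anticipated primary completion date.

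**The concern.** A study with 12-month assessments cannot end when the last participant's sample arrives, nor 5 months after a 15-month recruitment period closes, and still obtain those assessments from everyone. No section provides for data collection after the defined end, and section 10.2 places its time points within the study.

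The loss is administrative and depends on calendar date of entry. Any 1-year data would come only from early recruits. A shift over calendar time in who is recruited, or in how services are used, would then feed directly into the comparison of baseline with 1 year.

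Under some readings the primary endpoints are affected too. Sample receipt comes before DNA extraction, the array, genotyping, the PGx report and its return to the GP (section 10.3). The rate of recommendations and the prescribing decisions (section 15.1.1) do not exist until those steps are done.

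**Working it through.** **The plan's own figure.** September 2021 to April 2023, counted inclusively, is (2023 − 2021) × 12 + (4 − 9) + 1 = 20 months. This agrees with the 20 months in section 9.4, although April 2023 is labelled primary completion, not study end.

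**Inputs.** N = 500. Recruitment period A = 15 months (section 15b) or 20 months (one reading of the synopsis). Study end E = month 20, or about month 15 if the last sample governs with A = 15. Follow-up F = 12 months. L is the lag from consent to the start of the follow-up clock: 0 for anxiety and frailty, and the consent-to-review turnaround for the section 10.2 questionnaire. The Protocol gives no turnaround; time to the PGx result is itself a secondary endpoint. I use 2 months as an illustration.

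**Step 1, no accrual assumption.** The latest consent date that allows 1 year from consent is E − F = 20 − 12 = month 8. On the most favourable reading (A = 15, E = 20), the last recruit has 20 − 15 = 5 months.

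**Step 2, uniform accrual (my assumption).** Share unable to reach 12 months = 1 − (E − F − L)/A.

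| Reading | From consent (L = 0) | From review (L = 2) |
|---|---|---|
| A = 15, E = 20 | 1 − 8/15 = 47% (233) | 1 − 6/15 = 60% (300) |
| A = 20, E = 20 | 1 − 8/20 = 60% (300) | 1 − 6/20 = 70% (350) |
| A = 15, E = 15 (last sample) | 1 − 3/15 = 80% (400) | 1 − 1/15 = 93% (467) |

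**Step 3, sensitivity to accrual shape (A = 15, E = 20, L = 0).** If the cumulative share recruited by month t is (t/15)^k, the share missing is 1 − (8/15)^k: 27% for k = 0.5 (strongly front-loaded), 47% for k = 1 and 72% for k = 2 (back-loaded).

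**Step 4, participants with no medication review at study end.** With L = 2: 2/15 = 13% (67) if the study ends at the last sample after 15 months of recruitment; 2/20 = 10% (50) if recruitment runs to month 20; none if A = 15 and E = 20, because 5 months exceeds 2.

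**Step 5, the time point everyone can reach under a fixed month-20 end (A = 15).** At 6 months, (20 − 6)/15 = 93% reach it with L = 0, and (20 − 6 − 2)/15 = 80% with L = 2. At 3 months, all reach it provided 15 + L + 3 ≤ 20, that is L ≤ 2.

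**Step 6, the end date needed.** The last participant reaches 1 year from consent at 15 + 12 = month 27, or 20 + 12 = month 32. Add the turnaround where the clock starts at the review.

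**The case against.** The strongest reply is that this is a feasibility study and case series, that the 1-year measures are secondary, and that no primary endpoint is timed at 1 year. That is true and limits the damage, but the Protocol still lists these measures as endpoints and makes agreement to follow-up an inclusion criterion. The flow chart, patient journey and questionnaire file are not visible and may give a turnaround time. That could change the lagged figures, but not the rule in section 9.4.

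Four stronger readings are tempting and are not supported.

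- A reader might infer that the last recruits always lack a PGx result. With 15-month recruitment and a month-20 end they have 5 months, which may well be enough. The loss follows only under the last-sample trigger or recruitment to month 20.
- A reader might take a loss of about half or more as certain. It needs uniform accrual, and recruitment by database search does not settle the accrual shape.
- A reader might treat 20-month recruitment as established. The synopsis entry can equally mean 500 participants within a 20-month study.
- A reader might conclude that the claim in section 15b, of enough proof-of-principle data by the end of recruitment, fails. That section sets no threshold, and with a 2-month turnaround and uniform accrual 13/15 of 500, about 433, would have had a review by month 15.

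The lagged figures also apply only to assessments timed from the medication review. Anxiety and frailty run from consent.

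**Conclusion.** The rule is wrong as written. Under either trigger and either recruitment period, section 9.4 conflicts with the follow-up in sections 10.2 and 15.1.2. The month-8 cut-off under a month-20 end needs no assumption beyond recruitment starting when the study does.

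The proportion lost is conditional. It is 47% to 80% from consent under uniform accrual, depending on the reading; about 27% in the best case with strongly front-loaded accrual; and 60% to 93% for the review-clocked questionnaire at an assumed 2-month turnaround. Loss of recommendation and prescribing-decision data for the final recruits is a further consequence of two of the three readings, not of all.

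**What to change.** Define end of trial in section 9.4 as the last participant's 12-month assessment, meaning questionnaire plus record review. State one recruitment period in the synopsis and section 15b, and one clock origin (consent or medication review) across sections 10.2 and 15.1.2. Move the end date to at least month 27 for 15-month recruitment, plus turnaround if the clock starts at the review. The cost is one amendment and a later end date. The extra follow-up is questionnaires and record review only.

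If month 20 cannot move, keep the target of 500 and restate the 1-year endpoints as applying to participants with 12 months of potential follow-up. Give the expected number under a stated accrual pattern: for 15-month uniform recruitment and a month-20 end, 500 × 8/15 = about 267 from consent, or 500 × 6/15 = 200 at a 2-month lag. Section 9.4 must then say that month 20 governs. In that case 3 months is the latest scheduled time point all participants can reach, and only with 15-month recruitment and a turnaround of at most 2 months; 6 months is not reached by all. The cost is 1-year results from early recruits only, which should be said when they are reported.
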